#### **1.2.4.1.5. Protocol No. RZL-012-DD-P2bUS-001.4 Status: On-going**

Another study for DD patients, a double blind, randomized, multi-center, placebo-controlled phase 2b clinical trial for the evaluation of efficacy and safety of RZL-012 in subjects having DD, is being conducted under IND 135762.

The primary objective is to evaluate of the efficacy of RZL-012 following injection into lipomas/nodules of DD subjects. Efficacy is determined by ultrasound assessment of the lipoma/nodule dimensions after treatment as compared to baseline assessments.

The key secondary objective is the assessment of lipoma/nodule associated pain using the Comparative Pain Scale. Safety is assessed by the frequency of AEs and by change-from-baseline values for vital signs, clinical laboratory and ECG. An exploratory objective is to follow improvement in Quality of Life by using QOL questionnaire.

A total of 38 subjects have been enrolled into the study. Subjects were randomized in a 1:1 ratio into either the RZL-012 or the placebo arm.

At least 4 lipomas/nodules, preferably 6, and no more than 8, were injected per subject. Dosing was determined according to lipoma size, where the total injected dose did exceed 240 mg per patient (48 injections of 5mg/injection). Table 3 describes the dosages according to lipoma size.

**Table 3: Dosages According to Lipomas Size**

Number of Subjects – Active/Placebo	20/18				
Lipoma/Nodule size – diameter (cm)	1-1.9	2-3.9	4-5.9	6-7.9	8-10
Total Dose of RZL-012 in the RZL group (mg)	10	20	40	50	60
Number of Injections	2	4	8	10	12

The injections are spread randomly on the lipoma surface with a distance between injections of at least 1 cm. Injections are given at 90° to the injected skin surface.

Once the study ends and codes are opened, 84 days after dosing, placebo-treated subjects will be offered the option of receiving treatment with RZL-012. Subjects who choose to receive treatment with RZL-012 will be followed for an additional 84 days.

#### RZL-012-DD-P2b-US-001.4 Results:

All 38 subjects were enrolled and treated in accordance with the treatment arm to which they were randomized. Study results are pending.

Safety results to date have demonstrated a tolerable and good safety profile. There were no systemic or serious AEs were reported.

## 2.0 STUDY OBJECTIVES

### 2.1 Study Objectives

Raziel continues to investigate the efficacy and safety of RZL-012 for the treatment of SMF in a larger clinical population and conducted in a more controlled manner.

### **2.1.1 Primary Objective**

The primary objective of this study is as follows:

- to determine the efficacy of RZL-012 versus placebo on SMF reduction measured on Day 84 versus baseline using the Clinician Chin Assessment Tool (C-CAT).

### **2.1.2 Secondary Objectives**

The secondary objectives of this study are as follows:

- to determine the efficacy of RZL-012 versus placebo on SMF reduction measured on Day 84 versus baseline using both Subject Self-Chin Assessment Tool (S-CAT) and the Clinician Assessment Tool (C-CAT);
- to assess the reduction in SMF on Day 84 versus baseline using the caliper measured submental thickness and magnetic resonance imaging (MRI);
- to assess the safety of RZL-012 in the treatment of SMF reduction.

## **2.2 Description of Study Design**

This is a Phase 2b, double-blind, randomized, three-arm, placebo-controlled study that will consist of a screening period, baseline period, and a randomized treatment period.

Subjects will receive a single treatment session that consists of multiple injections of RZL-012 or placebo (Tween-80, propylene glycol, benzyl alcohol, and water) into the submental area under the chin, after which they will be monitored for safety and efficacy over 84 days.

Following the Day 84 visit of the last subject, subjects from three (3) chosen clinical sites will be followed up further twice up to a 1 year after injection to evaluate the long term safety and efficacy. The additional follow up visits will be at 6 and 12 months after injection.

For subjects from all sites that their adverse events were not resolved by Day 84, an unscheduled visit will be set 6-8 weeks after Day 84 to verify the resolution of the AE. On that visit, follow up of efficacy using C-CAT and S-CAT will also be conducted.

Each subject will be randomized to either active treatment (high or low dose RZL-012) or placebo at a ratio of 1:1:1 per group and receive one of the following:

- low dose (concentration of injected solution 34 mg/mL RZL-012) of 5.1 mg/0.15 mL/injection point that results in a dose/volume of  $163.2 \pm 20.4$  mg/4.8  $\pm 0.6$  mL RZL-012,
- high dose (concentration of injected solution 50 mg/mL RZL-012) of 7.5 mg/0.15 mL/injection point that results in a maximum total dose/volume of  $240 \pm 30$  mg/4.8  $\pm 0.6$  mL RZL-012,
- placebo of 0.15 mL/injection point that results in a total maximum volume of 4.8  $\pm 0.6$  mL.

Screening period: Subjects will undergo screening within 28 days prior to entering into the study.

Screening period will contain 2 visits, pre-screening visit to verify that subject qualifies the study based on S-CAT , C-CAT and 2D photography and another visit that will include an assessment of eligibility by measurement of SMF thickness using calipers, skin type by Fitzpatrick scale, subject's satisfaction scale related to appearance of SMF, subject impact questionnaire, and MRI. MRI will be conducted prior to the baseline visit. ECG and blood samples will also be conducted during the second screening visit.

Baseline treatment period: A total of 135 eligible male or female subjects will be randomized according to a predetermined randomization scheme (1:1:1 ratio) to receive a single multi-injection treatment of high dose RZL-012, low dose RZL-012, or placebo on Day 0. Subjects will be monitored for AEs and treatment area evaluation for 30 minutes post dose prior to discharge from the clinical trial site. Subjects will return to the site for study visits on Days 1, 7, 28, and 56 and for a final study visit on Day 84 for efficacy and safety assessments.

Subjects will be advised to continue their regular diet and physical activity during the study.

Blood samples will be collected at Day 1, 7, 28 and Day 84 study visits for assessment of hematology and serum chemistry. If there are clinically significant alerts obtained at any visit, , an unscheduled visit will be added for additional blood sampling.

Safety assessments will be performed at each study visit and subjects can be released after blood sampling and study assessments are completed.

Safety assessments include vital signs, ECG, blood samples, AE assessment, and treatment area evaluation. Treatment area evaluations including, but not limited to evaluation of edema, bruising, dysphasia, dysphonia, erythema, dyspigmentation, induration, numbness, pain, paresthesia , pruritus, skin ulceration and necrosis, injury to the marginal mandibular nerve, vascular and nerve injury and tissue damage to nearby vulnerable anatomic structures .. Concomitant medications will be recorded. An internal safety review committee will review the safety data collected during the study in a blinded manner. The committee members will include study medical monitor, Raziel's CMO and clinical director. The meeting will be held for every 40 subjects enrolled. Following completion of enrollment period, the committee will meet quarterly during the follow up period.

## **2.3 Study Endpoints**

### **2.3.1 Primary Endpoint**

The primary endpoint of this study is as follows:

- comparison of the proportion of subjects who have at least a 1-grade improvement in the C-CAT on Day 84 versus baseline between the RZL-012 high dose (270 mg/5.4 mL) group and the placebo group.

### **2.3.2 Secondary Endpoints**

The secondary endpoints of this study are as follows:

- Proportion of subjects who have at least a 1-grade improvement in both the C-CAT and S-CAT (Day 84 versus baseline) in the RZL-012 groups versus placebo group.
- Proportion of subjects who have at least a 2-grade improvement in both the C-CAT and S-CAT (Day 84 versus baseline) in the RZL-012 groups versus placebo group.
- Reduction in SMF volume by MRI (Day 84 versus screening) in the RZL-012 groups versus placebo group.
- Reduction in SMF thickness measured with caliper (Day 84 versus baseline) in the RZL-012 groups versus placebo group. Safety assessment of RZL-012 in the treatment of SMF reduction.
- safety of RZL-012 in the treatment of SMF reduction.

### **2.3.3 Exploratory Endpoints**

The exploratory endpoints of this study are as follows:

- SMF improvement using the Global Aesthetic Improvement Scale (GAIS).
- SMF improvement using the physician Global Assessment of Change Scale.
- SMF improvement using the Subjects Global Self-Assessment of Change Scale
- SMF improvement using the Subject Global Assessment of Change Scale.
- SMF improvement using the subject's satisfaction questionnaires.
- SMF improvement using Subject's impact questionnaire.

### **2.3.4 Randomization/Assignment to Study Drug**

A total of 135 eligible male or female subjects (45 subjects per group) will be randomized according to a predetermined randomization scheme (1:1:1 ratio) to receive a single multi-injection treatment of high dose RZL-012, low dose RZL-012, or placebo. Each subject will be randomized to receive one of the following:

1. RZL low dose – dose of  $163.2 \pm 20.4$  mg/subject spreads over  $32 \pm 4$  injection points.
2. RZL high dose – dose of  $240 \pm 30$  mg/subject spread over  $32 \pm 4$  injection points.
3. Placebo – volume of  $4.8 \pm 0.6$  ml vehicle/subject spread over  $32 \pm 4$  injection points.

## **2.4 Study Drugs**

### **2.4.1 Test Product and Dosing**

RZL-012 is a novel synthetic molecule provided as a sterile liquid solution suitable for injection.

All subjects will receive a single treatment of RZL-012 or placebo in multiple injections in accordance with the treatment cohort schedule as shown in Table 4 below:

**Table 4: Dosing Regimen**

[figure not shown]
	N=135		
	RZL-012 High dose (50mg/mL)	RZL-012 Low dose (34mg/mL)	Placebo
Number of subjects (N)	45	45	45
Maximum RZL-012 dose (mg)/volume (mL)	270mg/5.4 mL	183.6 mg/5.4 mL	0mg/5.4±0.6mL
RZL-012 Dose (mg)/volume (mL) per single injection	7.5mg/0.15mL	5.1mg/0.15mL	0mg/0.15mL
Number of Injections per subject	32±4, maximum of 36		

Subjects treated with RZL-012 will undergo a single treatment session with  $32\pm4$  injections. The maximal number of injections will be 36 with maximal doses of 183.6 mg and 270 mg for the low and high doses, respectively. Each injection point will be dosed with 5.1 mg RZL-012 for the low dose or 7.5 mg for the high dose in a volume of 0.15 mL/injection site. Placebo subjects will be injected with a 0.15 mL placebo per each injection site. The maximal injection volume for all groups will be up to 5.4 mL.

Subjects will be injected with RZL-012 or placebo perpendicularly ( $90^\circ$ ) to the skin. An ice pack will be placed on the injected area for pain relief immediately after injection. Subjects will remain seated in the injection position for an additional 10 minutes after dosing.

The injection pattern will be based on a submental area shaped grid in which the distance between rows and columns will be 1 cm, as seen in Figure 7 below. The Investigator will choose  $32\pm4$  sequential points on the grid that will mark the injected area according to SMF fullness and convexity. The treatment area boundary: superiorly by a line 1 cm inferior to the mandibular margin, laterally by the sternocleidomastoid muscles, and inferiorly by the hyoid bone.

**Figure 7: Scheme of Injection Pattern Grid**

An internal safety review committee will review the safety data collected during the study in a blinded manner. The committee members will include study medical monitor, Raziel's CMO and clinical director. The meeting will be held for every enrolled 40 subjects. Following completion of enrollment period, the committee will meet every quarterly during the follow up period.

#### **2.4.2 Dose Rationale**

The maximal RZL-012 dose tested in the SMF phase 2a study was 210 mg, which is 87.5% of the NOAEL. No serious AEs were associated with this dose per injection site (5mg, 0.1mL), with the distance maintained between injection sites (1cm) or with the maximal overall dose. A distance of 1 cm will allow a good distribution RZL-012 into the submental area.

The averaged doses that were injected during phase 2a study were based on injection of 32 injection points on the grid that were spread with a distance of 1cm between injection columns and rows of the SMF pattern. Therefore, in the current phase 2b study, an area which includes  $32 \pm 4$  injection points on the submental pattern grid was chosen.

For this study, two (2) doses have been chosen where the local injection volume is increased to 0.15 mL per injection site with a dose of 5.1 mg per injection site for RZL-012 low dose. Therefore, a maximal injection volume and dose will result in a maximal dose of 183.6 mg/5.4 mL into SMF area.

To increase the potential to demonstrate efficacy, a higher RZL-012 dose of RZL will also be assessed with a dose of 7.5 mg per injection site. Therefore, a maximal injection volume and dose for RZL-012 high dose will result in a maximal dose of 270 mg/5.4 mL into SMF area.

An increase from 240 mg which was determined as the NOAEL is justified based on available preclinical and clinical safety data of RZL-012.

Based on Kyebella's studies, injections up to 10 mL into the SMF area are acceptable.

#### **2.4.3 Serious Adverse Events Considered Related to the Investigational Drug**

AEs and serious adverse events (SAEs) will be monitored throughout the study.

Study discontinuation is to be considered by the investigator in any case of SAEs and the actions taken are to be fully documented in source documents and Case Report Forms (CRFs).

SAEs are considered to be related to the study drug.

Subjects experiencing an SAEs will be followed for their skin condition.

SAE should be reported within 24 hours to the medical monitor.

The study may also be prematurely terminated in any of the following cases:

- Recurring serious or severe Adverse Drug Reaction (ADR) clinically evaluated by PI as warranting study termination.
- A decision made by Sponsor/medical monitor and/or IRBEC and/or local regulatory agency to terminate the study

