--	---

	
meeting will be held for every enrolled 40 subjects. Following completion of enrollment period, the committee will meet quarterly during the follow up period.
 
The study enrollment will be suspended if either of the following occur:
 
 
• Greater than 20% of subjects report a drug related grade 3 (severe) adverse event for a period duration of more than 28 days after injection. Of note severe swelling is expected and may be present for the first 24-96 hours after injection.
 
• >1 subject with a drug related CTCAE Grade of 4 or 5
 
 
In the event of the above, the enrollment and treatment will be suspended, the safety committee will review all data to examine potential safety issue. Additional experts may be brought in to review safety data if deemed necessary by the safety committee. A safety report will be issued with the conclusions of the meeting. The recommendation of the safety committee will be documented. Potential outcomes are reinitiating enrollment with current safety practices, reinitiating study enrollment with caveats (e.g. additional precautions/limitations or safety training), stop enrollment.

Sample Size	
135 subjects (45 subjects per group):
 
 
1. RZL low dose – dose of <math>163.2 \pm 20.4</math> mg/subject spreads over <math>32 \pm 4</math> injection points
 
2. RZL high dose – dose of <math>240 \pm 30</math> mg/subject spread over <math>32 \pm 4</math> injection points
 
3. Placebo – volume of <math>4.8 \pm 0.6</math> ml vehicle/subject spread over <math>32 \pm 4</math> injection points
 

Study Population	
Adult volunteers age 18 to 65 years who have consented to participate in this study.

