### **5.0 SAFETY ASSESSMENTS**

#### **5.1 Collection of Adverse Events Data**

Data regarding treatment-emergent AEs (TEAEs) will be collected in this study. TEAEs are events that are not present at baseline, or if present at baseline, have worsened in severity. AEs will be assessed while the subjects are in the study. AEs assessed by the Investigator as related to study drug and “ongoing” at discharge will be monitored by the Investigator until resolved or until the subject is deemed “lost to follow-up”.

Any AEs reported by the subject or noted by the Investigator or his/her designee will be recorded on the eCRF regardless of the Investigator opinion of causality. The following information will be recorded for each AE: description of the event, date and time of onset, date and time of

resolution, severity, causal relationship to study drug, outcome, action taken with the study drug and any treatment given.

The AEs reported during the trial will be graded, documented, and assessed in regards to their clinical significance and relation to study drug. Treatment area evaluations including, but not limited to evaluation of edema, bruising, dysphasia, dysphonia, erythema, dyspigmentation, induration, numbness, pain, paresthesia, pruritus, skin ulceration and necrosis, injury to the marginal mandibular nerve, vascular and nerve injury and tissue damage to nearby vulnerable anatomic structures..

All abnormal changes from baseline will be collected, graded with regards to severity or clinical significance, assessed for causal relationship and recorded on the eCRF.

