The Investigator will assess AEs for severity, relationship to IP, and as to whether the event meets one or more of the definitions of an SAE. The assessments will be recorded on the source documents and AE CRF, using the categories defined below.

Causality Category	Description
Un-related	A clinical event, including laboratory test abnormality, with a temporal relationship to drug administration which makes a causal relationship improbable, and in which other drugs, chemicals or underlying disease provide plausible explanations. For the purpose of this protocol, the term unlikely will be considered not related to study medication and an “Adverse Event”.
Related	A clinical event, including laboratory test abnormality, with a reasonable time sequence to administration of the drug, but which could also be explained by concurrent disease or other drugs or chemicals. Information on drug withdrawal may be lacking or unclear. For the purpose of this protocol, an event that has possible or probable relationship to study medication will be defined as a “Suspected Adverse Drug Reaction”.

In order to classify AEs and diseases, preferred terms will be assigned by the sponsor or its designee to the original terms entered on the CRF, using MedDRA.

For those AEs that are not described on the CTCAE v 5.0, such AEs will be graded on a 5-point scale (mild, moderate, severe) and reported as indicated on the CRF. Intensity of such an AE is defined as follows:

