## 11.2 Serious Adverse Events

According to the ICH Guidelines for Good Clinical Practice (E6), an SAE is any untoward medical occurrence during the course of a clinical investigation that is characterized by one or more of the following:

- Results in death
- Is life-threatening
- Requires in-subject hospitalization or prolongation of existing hospitalization
- Results in persistent or significant disability/incapacity
- Is a congenital anomaly/birth defect
- Important medical events

Although not an SAE, exposure to study drug during pregnancy, even if no AE is reported in the mother, should be reported within 24 hours.

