### **11.2.4 Internal Safety Committee**

An internal safety review committee will review the safety data collected during the study in a blinded manner. The committee members will include study medical monitor, Raziel's CMO and clinical director.

The meeting will be held when every enrolled 40 subjects completed Day 7. Summary of the safety including all subjects up to that point may be reviewed as well. Following completion of enrollment of all subjects, the committee will meet quarterly during the follow up period.

The study enrollment will be suspended if either of the following occur:

- Greater than 20% of subjects report a drug related grade 3 (severe) adverse event for a period duration of more than 28 days after injection. Of note severe swelling is may be during the first 24 – 96 hours after injection.
- >1 subject with a drug related CTCAE Grade of 4 or 5

In the event of the above, the enrollment and treatment will be suspended, the safety committee will review all data to examine potential safety issue. Additional experts may be brought in to review safety data if deemed necessary by the safety committee. A safety report will be issued with the conclusions of the meeting. The recommendation of the safety committee will be documented. Potential outcomes are reinitiating enrollment with current safety practices, reinitiating study with caveats (e.g. additional precautions/limitations or safety training), stop enrollment.. For each internal safety committee meeting, report will be prepared by the medical monitor that include data about enrollment, list of SAEs, summary of AEs.

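### Protocol 2.4.3 attributes SAEs to the study drug outright, contradicting the investigator's separate causality judgement in 11.1; a minor drafting error, corrected in one sentence

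*Protocol*

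**What the plan says.** Protocol 2.4.3 carries a heading about SAEs considered related to the investigational drug. Its text opens by covering AEs and SAEs generally, asks the investigator to consider discontinuation in any case of SAEs, and then states that "SAEs are considered to be related to the study drug". It goes on to 24-hour reporting to the medical monitor and to grounds for terminating the study.

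Causality is dealt with elsewhere in the protocol:

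- Section 5.1 lists what is recorded for each AE, including "severity, causal relationship to study drug, outcome, action taken with the study drug and any treatment given".
- Section 11.1, under the definitions of adverse events and adverse drug reactions, says "The Investigator will assess AEs for severity, relationship to IP, and as to whether the event meets one or more of the definitions", meaning the SAE definitions. Its causality table has two categories, un-related and related, and adds that "For the purpose of this protocol, the term unlikely will be considered not related to study medication".
- Section 11.2 gives the SAE definition, beginning "an SAE is any untoward medical occurrence during the course of a clinical investigation", followed by the seriousness criteria.

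Drug-relatedness also has an operational use. Section 11.2.4 suspends enrollment if there is ">1 subject with a drug related CTCAE Grade of 4 or 5", and the synopsis repeats the rule. The SAP safety section tabulates seriousness and relation to treatment among the attributes of AEs.

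**The concern.** An investigator who judges a serious event un-related under 11.1 is told by 2.4.3 that the event is related. Both sections are operative safety text, and no passage says which prevails or describes the 2.4.3 sentence as a reporting convention.

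Two things depend on the answer. One is the relationship entry for each SAE, which feeds the AE tables. The other is the suspension rule, whose second limb counts only subjects with drug-related Grade 4 or 5 events. If every SAE is related by decree, the qualifier in that limb no longer separates anything.

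**Working it through.** No figure in the plan bears on this point, so the check is a comparison of the text.

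1. **Scope of the 2.4.3 sentence.** The sentence has no limiting words. The heading could limit it, but the surrounding text does not keep to that limit: the opening line, the discontinuation line and the 24-hour reporting line all apply to SAEs in general. If the heading did govern, the sentence would say only that related SAEs are related. It is therefore either wrong or empty.

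2. **Against 11.1.** Here relationship and SAE status are separate items in one list of judgements made by the investigator, and un-related is an available answer. An SAE can be un-related under 11.1 and cannot be under 2.4.3. This is a direct contradiction.

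3. **Against 5.1.** Causal relationship is a field completed for each event, and events are recorded whatever the investigator thinks of causality. A field with only one permissible value for SAEs would be odd. It would not be impossible, because a default could sit beside it. This is a poor fit, not a contradiction.

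4. **Against 11.2.** The SAE definition rests on seriousness and does not mention causality. Silence does not contradict 2.4.3, but it does mean that nothing in the definition makes an SAE related.

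5. **Effect on the suspension rule.** Table 5 defines Grade 4 by life-threatening consequences and Grade 5 by death. Both are seriousness criteria in 11.2, so such events are SAEs. Under 2.4.3 read literally, each of them is drug related. The condition "subject with a drug related CTCAE Grade of 4 or 5" in the synopsis, and its copy in 11.2.4, would then be met by more than one subject with any Grade 4 or 5 SAE, whatever the cause.

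6. **Effect on the tables.** Protocol 12.4 and the SAP safety section both tabulate relationship to treatment. If sites follow 11.1, these tables are unchanged. If they follow 2.4.3, unrelated SAEs appear as related.

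**The case against.** The best case for leaving the text alone has three parts.

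First, the sentence nearly repeats its heading and may only describe which SAEs the section is about. The termination bullet in the same section speaks of adverse drug reactions, a term that presupposes a causality judgement. This makes a drafting slip the likely explanation, but it does not make the sentence correct, because the rest of the section covers SAEs of any cause.

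Second, the working procedure is already clear. Section 11.1 says who judges causality, in which categories, and that the result goes on the source documents and the CRF. No CRF, committee or SAP text sends anyone to 2.4.3. This stands, and it is why the point is minor.

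Third, presuming SAEs to be related could be a deliberate safeguard. The protocol does not say so, and reporting does not need it: 11.2.1 requires every SAE within 24 hours without regard to causality.

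Some stronger readings should be resisted.

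- A reader might infer that 11.2 also contradicts 2.4.3. It is only silent on causality.
- A reader might take the words on the purpose of the protocol in 11.1 as defining the un-related category. In that row they govern only how the term unlikely is treated.
- A reader might infer that a safety signal could be missed. The error over-attributes events to the drug, and for each committee meeting a "report will be prepared by the medical monitor that include data about enrollment, list of SAEs, summary of AEs", so every SAE is listed there anyway.
- A reader might want a probability of a false suspension. That needs a rate of unrelated Grade 4-5 events, which the documents do not give.
- A reader might conclude that the suspension rule itself needs rewriting. The contradiction lies in 2.4.3. Defining drug related in the rule as the investigator's entry would be a separate, substantive choice, because it would bind a committee that the present text leaves room to judge.

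**Conclusion.** The point holds as a minor internal contradiction. The sentence in 2.4.3 is wrong as written against 11.1 and sits awkwardly with 5.1. It is probably a slip.

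The consequence arises only if someone applies the sentence literally: unrelated SAEs would be recorded as related, and every Grade 4-5 SAE would count toward suspension. That error is conservative. A trigger suspends enrollment and treatment pending a review, and resuming is among the listed outcomes. The primary and secondary efficacy analyses and the sample size are untouched.

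The conclusion rests on the wording alone and on no assumed event rate, so no numerical size is attached to it.

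**What to change.** In 2.4.3, delete the sentence, or replace it with: *The investigator will assess the relationship of each SAE to the study drug as described in Section 11.1.* Either version removes the contradiction, and the replacement also points the reader to the operative procedure.

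No change to 11.2.4 or the synopsis is needed. Once the sentence is gone, 11.1 is the only text that says how relationship is assessed.

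The cost is one sentence at the next amendment. The CRF, SAE reporting, sample size and SAP stay as they are.
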